4.4. Protocol Deviations

Subjects who did not meet the eligibility criteria for study entry, but enrolled in the study will be provided in a by-subject listing for those subjects who did not meet at least 1 eligibility (inclusion or exclusion) criterion. The listing will present the eligibility criterion (or criteria if more than 1 deviation) that subjects did not meet and related comments, if collected. A listing of subjects who received the wrong study treatment will also be provided.

Protocol deviations occurring after subjects entered the study are documented during routine monitoring. The number and percentage of subjects with important protocol deviations by deviation reason will be summarized by treatment group for the Randomized Analysis Set. A by-subject listing will be provided for those subjects with important protocol deviations.

5. BASELINE CHARACTERISTICS

5.1. Demographics and Baseline Characteristics

Subject demographic data (ie, age (years), age group (<6 and ≥ 6 years), sex, race, ethnicity, and geographic region (North America/Europe, and Asia)) and baseline characteristics (ie, weight (kg), height (cm), body mass index [BMI] (kg/m²), BMI categories (< 18.5 kg/m² [underweight], ≥ 18.5 - 25.0 kg/m² [normal], ≥ 25.0 - 30.0 kg/m² [overweight], and ≥ 30.0 kg/m² [obese])), and corresponding weight, height, and BMI Z-scores (calculated using the lambda-mu-sigma (LMS) method based on the Centers for Disease Control and Prevention (CDC) growth chart {[Centers for Disease Control and Prevention \(CDC\) 2016](#)}), will be summarized by treatment group and overall using descriptive statistics (sample size, mean, SD, median, Q1, Q3, minimum, and maximum) for continuous data and by the number and percentage of subjects for categorical data using the Safety Analysis Set. Age will be calculated in years at the date of first dose of study drug.

Baseline disease characteristics will include a summary of HBV DNA level (log₁₀ IU/mL), HBsAg (log₁₀ IU/mL), HBsAg status (positive [HBsAg ≥ 0.07 IU/mL], negative [HBsAg < 0.07 IU/mL]), HBeAg and HBeAb status (positive, negative), ALT and asparatate aminotransferase (AST) values (U/L), corrected BMD (via DXA scan) and corrected Z-Scores for both spine and whole body, serum bone biochemical markers including: urine bicarbonate, urine n-telopeptide, serum c-telopeptides, osteocalcin, bone specific alkaline phosphatase, PTH, vitamin D levels (25-hydroxy) and 1, 25 (dihydroxyvitamin) D levels, fasting serum creatinine and phosphate, spot urine creatinine and phosphate, and renal phosphate threshold (TmP/GFR), and estimated GFR by the Schwartz formula using the Safety Analysis Set.

In addition, the following baseline disease characteristics will be summarized:

- ALT level based on central laboratory normal range ($\leq 1.5 \times \text{ULN}$, $> 1.5 \times \text{ULN} - 5 \times \text{ULN}$, $> 5 \times \text{ULN} - 10 \times \text{ULN}$, $> 10 \text{ ULN}$)
- ALT level based on AASLD normal range (ULN is 30 U/L for pediatric subjects; $\leq 1.5 \times \text{ULN}$, $> 1.5 \times \text{ULN} - 5 \times \text{ULN}$, $> 5 \times \text{ULN} - 10 \times \text{ULN}$, $> 10 \text{ ULN}$)
- Previous Hepatitis B medication exposure (yes, no)
- Years positive for HBV
- HBV genotype (A, B, C, D, etc.); if genotype results at baseline are missing, genotype results post-baseline, if available, will be reported in this summary

By-subject listings will be provided to support the summaries of demographics and baseline characteristics and baseline disease characteristics tables.

For categorical data, the Cochran-Mantel-Haenszel (CMH) test (general association statistic for nominal data, and row means scores differ statistic for ordinal data) will be used to compare the 2 treatment groups. For continuous data, the 2-sided Wilcoxon rank sum test will be used to compare the 2 treatment groups.

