4.2. Inclusion Criteria

Subjects must meet *all* of the following inclusion criteria to be eligible for participation in this study.

- Male or female
- 2 years to < 12 years of age (consent of parent or legal guardian required)
- Body weight $\geq 10\text{kg}$
- Documented chronic HBV infection, defined as positive serum HBsAg ≥ 6 months
- HBeAg-positive or HBeAg-negative
- HBV DNA $\geq 10^5$ copies/mL (PCR method)
- ALT $\geq 1.5 \times \text{ULN}$ at screening
- Estimated glomerular filtration rate (creatinine clearance) $\geq 80 \text{ mL/min/1.73m}^2$

Estimated creatinine clearance using Schwartz Formula
(mL/min/1.73m^2) = $k \times L/\text{Scr}$

[(k is proportionality constant: pediatric males/females ≥ 2 years to < 12 years $k = 0.55$; for adolescent females ≥ 12 years old, $k = 0.55$, and for adolescent males ≥ 12 years, $k = 0.70$); L is height in centimeters (cm); and Scr is serum creatinine (mg/dL)]

- Adequate hematologic function (absolute neutrophil count $\geq 1,500/\text{mm}^3$; hemoglobin $\geq 10.0 \text{ g/dL}$)
- Negative serum β -HCG pregnancy test (for females of childbearing potential only)
- Male and female subjects of childbearing potential (defined in Section 7.7.1) identified as choosing to become sexually active must agree to utilize highly effective contraception methods or agree to abstain from heterosexual intercourse while on study treatment and for 30 days following the last dose of study drugs (refer to Section 7.7.2).

- Parent or legal guardian able to provide written informed consent prior to any screening evaluations and willing to comply with study requirements
- Subject able to provide written assent as determined by IRB/IEC/local requirements and Investigator's discretion.
- No prior tenofovir DF therapy (subjects may have received prior interferon-alfa and/or other oral anti-HBV nucleoside/nucleotide therapy; subjects must have discontinued interferon-alfa therapy ≥ 6 months prior to screening; subjects experienced on other anti-HBV nucleoside/nucleotide therapy must have discontinued therapy ≥ 16 weeks prior to screening to avoid flare if randomized to the placebo arm)

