6.4. Changes From Protocol-Specified Efficacy Analyses

The protocol specifies that the analysis of the primary efficacy endpoint will evaluate the difference between the TDF and placebo treatment groups using a two-sided Fisher's exact test. This has been modified to a CMH test, controlling for the age group at baseline and region, in order to account for the stratified randomization used in the study. The age group at baseline was specified as <6 vs. ≥6 years, compared to the randomization strata age group of 2 to <6 and 6 to <12 years, as some subjects were age 12 by baseline. This change was also made for the analyses of the secondary endpoints. The two-sided Fisher's exact test will still be performed as a secondary analysis of the primary endpoint.

The PP Analysis Set, Serologically Evaluable FAS for HBeAg Loss/Seroconversion, and Serologically Evaluable FAS for HBsAg Loss/Seroconversion, was not defined in the protocol, but was added in the SAP.

For HBV DNA analyses, the default will be to report measurements in IU/mL, which is the current clinically accepted way to describe this parameter, instead of copies/mL.

For ALT normalized and normal analyses, both the AASLD and central lab normal ranges will be used.

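### The baseline table sorts children by one fixed BMI scale with no age term, so under plausible assumptions more than half would be labelled underweight beside age-referenced Z-scores.

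*SAP*

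**What the plan says.** SAP Section 5.1 lists BMI categories among the baseline characteristics. The first is given as "BMI categories (< 18.5 kg/m² [underweight" and the others as "≥ 18.5 - 25.0 kg/m² [normal], ≥ 25.0 - 30.0 kg/m² [overweight], and ≥ 30.0 kg/m² [obese". No age or sex adjustment is attached to them. The SAP's two lists of changes from the protocol (Sections 6.4 and 7.11) do not qualify them either.

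The same sentence adds Z-scores for weight, height and BMI, "calculated using the lambda-mu-sigma (LMS) method based on the Centers for Disease Control and Prevention (CDC) growth chart".

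Section 5.1 then plans between-arm tests. Categorical baseline data get a CMH test, with the "row means scores differ statistic for ordinal data) will be used to compare the 2 treatment groups". Continuous data get a Wilcoxon rank sum test. By-subject listings support the baseline tables.

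Protocol Section 4.2 admits children from 2 to under 12 years. SAP Section 6.4 adds a small qualification, "as some subjects were age 12 by baseline". Protocol Section 8.7 asks for a summary of BMI at baseline and defines no categories. SAP Section 7.6 summarises BMI and its Z-score at each visit, again without categories.

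**The concern.** A fixed BMI cut-off carries the same meaning at every age only if typical BMI does not vary with age. By using growth-chart Z-scores, the SAP treats BMI in this population as age-dependent. The fixed labels do not. A child could therefore have an unremarkable BMI Z-score in one row of the table and count as underweight in another.

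At stake is a correct description of the trial population in one row of the baseline table. The CMH comparison of that row would also be affected, because it would compare the arms on a classification that does not measure nutritional status in children.

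**Working it through.** The plan states no expected distribution over the BMI categories, so there is no figure of its own to reproduce. Three checks were made.

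**1. What the cut-off demands, at the documents' own weights.** A child avoids the underweight label only if weight / height² is at least 18.5, that is, if height is at most √(weight / 18.5). The weights below are the 10 kg entry minimum (Protocol Section 4.2) and boundaries from the dosing tables (Protocol Tables 5-1 and 5-2).

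| Weight (kg) | Tallest height that avoids the label (cm) |
|---|---|
| 10 | 73.5 |
| 14 | 87.0 |
| 17 | 95.9 |
| 22 | 109.0 |
| 28 | 123.0 |
| 35 | 137.5 |

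For example, √(22 / 18.5) = 1.090 m. Any taller child of that weight is labelled underweight.

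**2. Illustrative children.** The heights and weights here are assumed; they do not come from the documents. The weight needed to leave the underweight class is 18.5 × height².

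| Height (cm) | Weight needed (kg) | Assumed weight (kg) | BMI (kg/m²) |
|---|---|---|---|
| 85 | 13.4 | 12 | 16.6 |
| 105 | 20.4 | 17 | 15.4 |
| 125 | 28.9 | 25 | 16.0 |
| 145 | 38.9 | 37 | 17.6 |

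All four would be labelled underweight.

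**3. Share of children labelled underweight.** In any group whose median BMI is below 18.5, more than half are below the cut-off by the definition of a median. To give a size, take BMI as lognormal, with the coefficient of variation (CV) used as the standard deviation of log BMI:

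share = Φ( ln(18.5 / median) / CV ).

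Median and CV are assumptions, shown as a range because the documents give no reference values.

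| Assumed median (kg/m²) | CV 8% | CV 11% | CV 15% |
|---|---|---|---|
| 15 | 100% | 97% | 92% |
| 16 | 97% | 91% | 83% |
| 17 | 85% | 78% | 71% |
| 18 | 63% | 60% | 57% |
| 18.5 | 50% | 50% | 50% |

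Worked line: for median 17 and CV 15%, ln(18.5 / 17) = 0.0846, 0.0846 / 0.15 = 0.564, and Φ(0.564) = 0.71. Over medians of 15 to 18 the share runs from 57% to 100% (rounded).

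**The case against.** The strongest reply is that the same section already supplies the right measure. Continuous BMI and BMI Z-scores are in the table, both are compared between arms by the Wilcoxon test, and the by-visit summaries use no categories. This stands. It limits the harm to one labelled row, its test and the listings. A reader might infer that the report as a whole would portray an underweight population; the Z-scores in the same table prevent that.

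A reader might also infer that almost every child would land in one class, leaving the CMH test with nearly nothing to compare. The documents do not establish this. It follows only at the lower assumed medians; at 17 to 18 kg/m² the share is 57% to 85%. Protocol Section 6.6 also seeks 12 pharmacokinetic subjects at each tablet strength, including 300 mg, which Table 5-1 assigns to children of at least 35 kg. A 35 kg child avoids the label up to 137.5 cm. A recruitment target is not a count, but heavier children were sought.

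Finally, a reader might link the labels to the bone results, since nutritional status bears on bone density. No planned analysis makes that link. Percent change in bone mineral density is compared by ANOVA with treatment as the only effect, and the Z-score shift analysis adjusts for baseline status (SAP Section 7.3.1). BMI category is not a stratum (Section 3.3) or a subgroup (Section 3.4).

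Nor do the labels contradict the Z-scores for every child. They conflict only where BMI is below 18.5 and the Z-score is unremarkable, and the number of such children cannot be known without the data.

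**Conclusion.** The point holds as a minor reporting error. One fixed BMI scale is applied to subjects from 2 years up to, in some cases, 12 years, in the same sentence that derives an age-referenced BMI measure. Under assumed medians of 15 to 18 kg/m² and CVs of 8% to 15%, about 57% to 100% of children would be labelled underweight. The conclusion that a majority would be so labelled fails only if the median BMI in this population is about 18.5 or more.

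The row and its CMH comparison would be misleading as written. The consequence is confined to the descriptive baseline table and its listings. The primary and key secondary analyses, the bone analyses, power and alpha are untouched.

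**What to change.** Delete the fixed BMI categories from SAP Section 5.1 and keep continuous BMI and the BMI Z-score. Alternatively, define the categories as BMI-for-age Z-score or percentile bands from the CDC growth-chart program listed in the SAP references. If any bands are kept, write them as non-overlapping intervals; as printed, 25.0 and 30.0 can each be read as belonging to two classes.

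The cost is one changed row definition. The Z-scores are already to be derived, and the protocol requires no BMI categories, so no protocol amendment is needed.

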5.2. Medical History

Medical history will be collected at screening for disease-specific and general conditions (ie, conditions not specific to the disease being studied).

A listing of medical history data will be provided for the Randomized Analysis Set.

6. EFFICACY ANALYSES

For Week 48 analyses, efficacy data will be summarized only for the double-blind phase. Two approaches will be used: (1) a Missing = Failure (M = F) approach and (2) a Missing = Excluded (M = E) approach. Unless otherwise specified, for the M=F approach, data will be summarized and p-values will be calculated up to Week 48, and for the M=E approach, data will be summarized up to Week 72 and p-values will be calculated up to Week 48. Sensitivity analysis of the primary efficacy endpoint will also be performed to evaluate the impact of the change in the endpoint from Week 72 to Week 48 in Protocol Amendment 3. All efficacy data up to the Week 48 data cut, including data collected during open-label phase and the treatment-free follow-up phase, will be provided in the listings.

For the Week 48 analysis, only the results from the HBV DNA PCR-based assay (both the undiluted and diluted version) will be reported in summaries and listings for analyses related to HBV DNA.

6.1. Primary Efficacy Endpoint

6.1.1. Definition of the Primary Efficacy Endpoint

The primary efficacy endpoint is the proportion of subjects with HBV DNA < 69 IU/mL (400 copies/mL) at Week 48. The Missing = Failure (M = F) approach will be employed for handling missing data.

6.1.2. Statistical Hypothesis for the Primary Efficacy Endpoint

The statistical hypotheses for the primary endpoint are as follows:

- **Null hypothesis:** the difference (TDF – placebo) in the proportions of subjects with HBV DNA < 69 IU/mL [400 copies/mL] at Week 48 is equal to 0
- **Alternative hypothesis:** the difference (TDF – placebo) in the proportions of subjects with HBV DNA < 69 IU/mL [400 copies/mL] at Week 48 is not equal to 0

6.1.3. Analysis of the Primary Efficacy Endpoint

The primary efficacy analysis will be conducted after the last randomized subject reaches Week 48 or discontinues study drug prematurely. The M = F approach will be employed for all data up to Week 48 using the Full Analysis Set. In this approach, all missing data will be treated as not having achieved the primary endpoint.

The analysis will evaluate the difference between treatment arms in the proportion of subjects achieving the primary endpoint, using a two-sided stratified Cochran-Mantel-Haenszel (CMH) test controlling for age at baseline (<6 and ≥6 years) and region (North America/Europe and Asia).

6.1.4. Secondary Analysis for the Primary Efficacy Endpoint

The following secondary analyses will be performed for the primary endpoint:

- Repeat the primary analysis using an unadjusted two-sided Fisher's exact test instead of the stratified CMH test
- Repeat the primary analysis using the Per Protocol Analysis Set instead of the Full Analysis Set
- Repeat the primary analysis using the M = E approach instead of the M = F approach. In this approach, all missing data will be excluded in the computation (ie, missing data points will be excluded from both the numerator and denominator).
- Assess the homogeneity of the odds ratio at Week 48 across age at baseline (<6 and ≥6 years) and region (North America/Europe and Asia) using the Breslow-Day test and the M = F approach

6.1.5. Sensitivity Analysis of the Primary Efficacy Endpoint

Sensitivity analyses will be performed to evaluate the impact of the change in the primary endpoint from Week 72 to Week 48, using both the M=F and M=E approach.

The primary analysis of the primary efficacy endpoint at Week 48 will be performed for the following subject groups using the FAS:

- Group 1: Subjects who completed the Week 48 assessment or prematurely discontinued from blinded study drug prior to Protocol Amendment 3
- Group 2: Subjects who completed the Week 48 assessment or prematurely discontinued from blinded study drug after Protocol Amendment 3
- Group 3: Group 1 subjects who also completed the Week 72 assessment or prematurely discontinued from blinded study drug prior to Protocol Amendment 3

To identify the first two groups, the Blinded Study Drug Form eCRF data will be used. Group 1 subjects who completed the Week 48 assessment prior to Protocol Amendment 3 will have data recorded using the original Blinded Study Drug form, while Group 2 subjects who completed the Week 48 assessment after Protocol Amendment 3 will have data recorded using the updated Blinded Study Drug after Protocol Amendment 3 was in place. Group 3 subjects will be identified by checking which Group 1 subjects had also completed Week 72 or discontinued blinded study drug on or prior to the official completion date of Protocol Amendment 3 of 29 February 2016.

Summaries of HBV DNA for Group 1 and Group 3 will be reported up to Week 72, and for Group 2 will be reported only up to Week 48. Only for the analysis of Group 1 subjects who completed the Week 48 assessment or prematurely discontinued from blinded study drug prior to Protocol Amendment 3, will p-values be calculated up to Week 72 using the stratified CMH test. P-values will not be reported for the other two analyses of Group 2 and Group 3 due to small sample sizes.

6.1.6. Subgroup Analysis for the Primary Efficacy Endpoint

The analysis of the proportion of subjects who achieved HBV DNA < 69 IU/mL [400 copies/mL] at Week 48 will be repeated within each subgroup specified in Section 3.4 using the FAS with the Missing = Failure approach. If a strata is one of the subgroup factors, as is the case for the subgroups analyses of region and age at baseline, then only the non-subgroup factor strata will be used when performing the stratum-adjusted CMH test.

6.2. Secondary Efficacy Endpoints

6.2.1. Definition of Secondary Efficacy Endpoints

The key secondary efficacy endpoint is as follows:

The proportion of subjects with HBeAg seroconversion at Week 48 in the Serologically Evaluable FAS for HBeAg Loss/Seroconversion.

For Week 48, secondary efficacy endpoints to be evaluated in all subjects in FAS include:

- proportion of subjects with normal ALT and normalization of ALT
- composite endpoint of proportion of subjects with HBV DNA < 69 IU/mL [400 copies/mL] and normal ALT
- proportion of subjects with HBV DNA < 29 IU/mL [169 copies/mL]
- proportions of subjects with HBsAg loss and seroconversion in the Serologically Evaluable FAS for HBsAg Loss/Seroconversion
- sequence changes from baseline within the HBV polymerase for subjects who were viremic (HBV DNA \geq 69 IU/mL [400 copies/mL]) at Weeks 48, 96, 144, 192 or Early Discontinuation; including subjects with confirmed virologic breakthrough

Other endpoints of interest

For Week 48, secondary efficacy endpoints to be evaluated in the Serologically Evaluable FAS for HBeAg Loss/Seroconversion include:

- proportion of subjects with HBeAg loss

- composite endpoint of proportion of subjects with HBV DNA < 69 IU/mL [400 copies/mL], normal ALT and HBeAg loss
- composite endpoint of proportion of subjects with HBV DNA < 69 IU/mL [400 copies/mL], normal ALT, and HBeAg seroconversion

For Week 48, secondary efficacy endpoints to be evaluated in subjects in the FAS with abnormal ALT at baseline include:

- proportion of subjects with normalized ALT
- composite endpoint of proportion of subjects with HBV DNA < 69 IU/mL [400 copies/mL] and normalized ALT

For Week 48, secondary efficacy endpoints to be evaluated in subjects in the Serologically Evaluable FAS for HBeAg Loss/Seroconversion with abnormal ALT at baseline include:

- composite endpoint of proportion of subjects with HBV DNA < 69 IU/mL [400 copies/mL], normalized ALT and HBeAg loss
- composite endpoint of proportion of subjects with HBV DNA < 69 IU/mL [400 copies/mL], normalized ALT, and HBeAg seroconversion

For the Week 48 analysis, the following definitions will be used:

- HBsAg loss is defined as quantitative HBsAg < 0.07 IU/mL result at a postbaseline visit with baseline HBsAb negative or missing and HBsAg \geq 0.07 IU/mL at baseline.
- HBsAg seroconversion is defined as HBsAg loss and a HBsAb test result change from HBsAb negative or missing at baseline to HBsAb positive at a postbaseline visit
- HBeAg loss is defined as a HBeAg test result change from HBeAg positive at baseline to HBeAg negative at a postbaseline visit with baseline HBeAb negative or missing
- HBeAg seroconversion is defined as HBeAg loss and a HBeAb test result change from HBeAb negative or missing at baseline to HBeAb positive at a postbaseline visit
- ALT normalization is defined as ALT greater than the upper limit of normal (ALT > ULN) as defined by the central laboratory normal range or AASLD normal range at baseline, but within normal range at a postbaseline visit

Borderline serology results will be imputed using the following rules:

- HBeAg borderline will be considered as HBeAg positive
- HBsAb and HBeAb borderline will be considered as HBsAb negative and HBeAb negative

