3.1.5. Serologically Evaluable Full Analysis Set

3.1.5.1. Serologically Evaluable Full Analysis Set for HBeAg loss/seroconversion

The Serologically Evaluable Full Analysis Set for HBeAg loss/seroconversion will include all subjects who were randomized and had received at least 1 dose of study drug, and with HBeAg positive and HBeAb negative or missing at baseline. Subjects will be analyzed according to the treatment to which they were randomized.

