3.8.3. Selection of Data in the Event of Multiple Records in a Window

Depending on the statistical analysis method, single values are required for each analysis window. For example, change from baseline by visit usually requires a single value, whereas a time-to-event analysis would not require 1 value per analysis window. When a single value is needed, the following rule(s) will be used.

For baseline of the double-blind and open-label phases, the last available record on or prior to the first dose of blinded and open-label study drug will be selected, respectively. If there are multiple records with the same time or no time recorded on the same day for numeric observations, the average will be computed for that day, except for HBV DNA [IU/mL] and quantitative HBsAg [IU/mL], where the geometric mean will be computed instead. If there are multiple records with the same time or no time recorded on the same day for categorical observations, the most conservative value will be taken, eg, negative will be selected over positive for HBeAg, and positive will be selected over negative for HBeAb and HBsAb.

The following specified rules will be used for postbaseline visits:

- **ALT:** The largest value will be included in the analysis when 2 or more ALT values occur within the same visit window.
- **BMD:** The latest record in the window will be selected.

- **HBV DNA and quantitative HBsAg:** The record closest to the nominal day for that visit will be selected. If there are 2 records equidistant from the nominal day, the latest will be selected. If there is more than 1 record on the selected day, the geometric mean will be taken.
- **Serology:** For HBeAg, HBeAb, and HBsAb, the record closest to the nominal day for that visit will be selected. If there are 2 records equidistant from the nominal day, the latest will be selected. If there is more than 1 record on the selected day, the most conservative value will be taken, ie, positive will be selected over negative for HBeAg, and negative will be selected over positive for HBeAb and HBsAb.

For all other laboratory parameters:

- If multiple valid non-missing numeric observations exist in a window, then records will be chosen as follows:
 - The record closest to the nominal day for that visit will be selected. If there are 2 records equidistant from the nominal day, the latest will be selected. If there is more than 1 record on the selected day, the average will be taken.

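### The borderline serology rule is conservative after baseline but not at baseline, where it can admit a child with borderline HBeAg to the evaluable set and later count that child as a seroconverter

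*SAP*

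**What the plan says.** SAP 6.2.1 introduces the rule with "Borderline serology results will be imputed using the following rules". The two rules are "HBeAg borderline will be considered as HBeAg positive" and "HBsAb and HBeAb borderline will be considered as HBsAb negative and HBeAb negative". Neither names a visit, so both reach baseline results.

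Baseline status does two jobs for the key secondary endpoint:

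- **Denominator.** SAP 3.1.5.1 restricts the evaluable set to treated children "with HBeAg positive and HBeAb negative or missing at baseline".
- **Starting point of the event.** SAP 6.2.1 defines HBeAg loss as a "HBeAg test result change from HBeAg positive at baseline to HBeAg negative at a postbaseline visit with baseline HBeAb negative or missing". It adds that "HBeAg seroconversion is defined as HBeAg loss and a HBeAb test result change from HBeAb negative or missing at baseline to HBeAb positive" at a later visit.

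For several same-day baseline records, SAP 3.8.3 takes the most conservative value, so that "negative will be selected over positive for HBeAg, and positive will be selected over negative for HBeAb and HBsAb". For postbaseline visits the same section reverses the order: HBeAg positive wins, and antibody negative wins.

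The protocol (synopsis; Section 6.1.2; footnote g of the Appendix 2 procedures table) makes HBeAb a reflex test, run when HBeAg is negative. SAP 3.5 makes HBeAg seroconversion at Week 48 the only secondary endpoint in the gatekeeping sequence, tested at 0.05 once the primary succeeds.

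**The concern.** A conservative convention for an uncertain result has to change direction between baseline and follow-up. After baseline, calling borderline HBeAg positive and borderline HBeAb negative withholds the event. At baseline the same coding makes a child eligible for the event.

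A child whose entry result was indeterminate is then handled exactly like one who was clearly HBeAg positive and antibody negative. If the Week 48 results are clear in the other direction, the full change is credited to the study period although the starting point was uncertain. The allowance for missing HBeAb widens the opening: if a borderline HBeAg does not trigger the reflex test, the child has no baseline HBeAb and is still admitted.

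At stake is the classification of events in the one gated secondary endpoint. The same baseline coding also feeds HBeAg loss and the four composites in SAP 6.2.1 that use HBeAg loss or seroconversion. Borderline HBsAb at baseline raises the same issue for HBsAg seroconversion.

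**Working it through.** **1. Trace one child through the rules.** Suppose HBeAg is borderline and HBeAb borderline or untested at baseline, with HBeAg negative and HBeAb positive at Week 48.

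| Step | SAP section | Result |
|---|---|---|
| Baseline HBeAg recoded | 6.2.1 | positive |
| Baseline HBeAb recoded or absent | 6.2.1 | negative or missing |
| Evaluable set | 3.1.5.1 | included |
| HBeAg loss at Week 48 | 6.2.1 | yes |
| HBeAg seroconversion at Week 48 | 6.2.1 | yes |

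Under the baseline direction of 3.8.3, the same child would be HBeAg negative and outside the set.

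**2. Look for a safeguard.** SAP 6.2.2 repeats the analyses under M = F and M = E. SAP 6.3 repeats the endpoint in children who reached Week 48 or stopped blinded drug before Amendment 3. No planned analysis recodes, excludes or counts children who were borderline at baseline.

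**3. Direction of the effect.** The plan gives no rate for this endpoint and no count of borderline results, so these inputs are assumed: true seroconversion 20% on TDF and 10% on placebo; a share b of evaluable children borderline at baseline, equal in both arms; and a probability q, equal in both arms, that such a child meets the definition.

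Observed rate = (1 − b) × true rate + b × q. Difference = (1 − b) × 10 points.

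| b | q | TDF | Placebo | Difference |
|---|---|---|---|---|
| 2% | 50% to 80% | 20.6% to 21.2% | 10.8% to 11.4% | 9.8 points |
| 5% | 50% to 80% | 21.5% to 23.0% | 12.0% to 13.5% | 9.5 points |
| 10% | 50% to 80% | 23% to 26% | 14% to 17% | 9.0 points |

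Both rates rise and the difference shrinks slightly. If the arms share one rate, they still share one after this misclassification. At common rates of 10% to 20% with an assumed 60 vs 29 evaluable, Fisher's exact test rejects 3.0% to 3.5% of the time, below 5%.

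**4. Weight of one child.** SAP 6.2.2 plans a CMH test stratified by age and region. Stratum counts are not given, so the check uses one stratum. The evaluable numbers, 54 and 27, are assumed; 89 children were treated (SAP 1.3). One child is 1/54 = 1.9 points on TDF or 1/27 = 3.7 points on placebo. With 60 vs 29 these become 1.7 and 3.4.

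For a events among n on TDF, t events in total, and m on placebo, with N = n + m:

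Q = (a − nt/N)² / [nmt(N − t) / (N²(N − 1))], referred to chi-square with 1 df.

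- 10/54 vs 1/27: expected 54 × 11/81 = 7.333, variance 2.139, Q = 3.325, p = 0.068.
- 11/54 vs 1/27: expected 54 × 12/81 = 8.000, variance 2.300, Q = 3.913, p = 0.048.
- 13/54 vs 1/27: expected 54 × 14/81 = 9.333, variance 2.606, Q = 5.160, p = 0.023.
- 13/54 vs 2/27: expected 54 × 15/81 = 10.000, variance 2.750, Q = 3.273, p = 0.070.

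The proposed fix removes the child from the denominator as well. Then 11/54 vs 1/27 becomes 10/53 vs 1/27, with p = 0.064, and 13/54 vs 2/27 becomes 13/54 vs 1/26, with p = 0.027. One child can cross 0.05 in either direction.

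**The case against.** Several stronger readings are tempting, and the documents do not support them.

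- **That the rule favours TDF or inflates type I error.** It is identical in both blinded arms. Step 3 shows a slight dilution on average, and step 4 shows that a placebo event works against TDF.
- **That Fisher p-values show the fragility.** Fisher's test gives 0.051 for 12/54 vs 1/27 and 0.028 for 13/54 vs 1/27. But SAP 6.4 moves the secondary endpoints to CMH and keeps Fisher only as a secondary analysis of the primary endpoint. Single-stratum CMH gives 0.033 and 0.023, both below 0.05.
- **That the SAP contradicts itself.** Section 3.8.3 settles multiple same-day records; 6.2.1 maps a borderline category. They differ in direction but do not govern the same case.
- **That a borderline child is already losing HBeAg, or needs only a small later shift.** The documents do not say what a borderline result means clinically. The event needs an outright negative HBeAg and an outright positive HBeAb; a borderline result on either test at that visit blocks it.

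It is also fair that any small binary endpoint has a one-child boundary, that reflex testing may make the double-borderline baseline rare, and that spontaneous change occurs in both arms and is accounted for by the randomized comparison. These points limit the size of the problem. They do not change the trace in step 1, and an untested HBeAb still leaves the child evaluable.

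**Conclusion.** The point stands as a minor one. As written, the rule reaches baseline, and there it works against the conservative direction the SAP uses elsewhere. A child with an indeterminate baseline can be counted as a seroconverter, and no planned analysis would show it.

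The expected consequence is some misclassified events, somewhat higher rates in both arms and a slightly smaller difference: 9.0 to 9.8 points instead of 10 under the assumptions shown. Significance could turn on one child, in either direction, only if the result falls near 0.05.

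This rests on assumed evaluable numbers, an unstratified version of the planned test, and equal behaviour of borderline children in both arms. The number affected is unknown and may be zero.

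**What to change.** Add one sentence to SAP 6.2.1 that makes the rule depend on the visit. After baseline, keep it as it is. At baseline, count borderline HBeAg as negative and borderline HBeAb or HBsAb as positive, so that the child is not evaluable for the corresponding endpoint. This matches the direction in 3.8.3.

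Decide it before unblinding, which fits SAP 3.1, where membership of the analysis sets is settled before the blind is broken. Report the number of baseline-borderline results by arm, and give the analysis under the current rule as a sensitivity analysis.

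The cost is a sentence, a small count table and one repeated analysis. The downside is that a few children who may be truly HBeAg positive could leave the evaluable set; the sensitivity analysis shows whether that matters.
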